**Pulmonary Function Testing and Lung Volumes:**

Pulmonary Function Test: While seated in the chair and after a mouth piece and nose clip are applied, the subject will be asked to breathe normally for 3 to 6 breaths. They will then be instructed to forcibly inhale until their lungs are filled. After a brief pause, they will then be instructed to forcibly exhale the air in their lungs and hold the maneuver for approximately 6 seconds. After a brief rest, the maneuver will be repeated a minimum of three times to ensure reliability.

Static Lung Volumes: The volume of air in the lungs will be assessed using the nitrogen washout technique. The nitrogen washout technique, which takes about five minutes to perform, will begin while a subject is seated in his/her wheelchair and after a mouth piece and nose-clips have been applied. The subject will then be asked to breathe room air into and out of the mouthpiece for 3-6 breaths. The air exhaled, which normally contains mostly nitrogen, will be collected and analyzed by a machine called a metabolic cart. Once a subject has completed the 3-6 breaths, he/she will be asked to take a slow deep breath in and to exhale until he/she feels that the lungs are empty, after which the subject returns to a normal breathing pattern. Following an additional 3-6 regular breaths, the metabolic cart will begin delivering 100% oxygen through the mouthpiece. The subject will continue to inhale 100% oxygen while taking normal breaths until oxygen is the only gas measurable in his/her exhaled air. After a brief rest, the maneuver will be repeated a minimum of two times to ensure reliability.

**Respiratory Muscle Strength Testing:** Maximal inspiratory pressure (MIP) from functional residual capacity (FRC), and maximal expiratory pressure (MEP) from TLC will be performed with a flanged mouthpiece according to established protocols using a modification of the Black and Hyatt technique [36]. For simultaneous measurement of transesophageal pressures, subjects will be asked to swallow a small balloon-tipped catheter connected to a computer. The balloon will be inserted into one nostril and into the esophagus after numbing medicine (4% lidocaine) has been applied to the nasal passages, throat, and to the tube itself in order to make swallowing the balloon easier. Then, pressures at the mouth and at the balloon will be recorded simultaneously by having the subject blow in and out as strongly as possible through a mouthpiece connected to a recording device. The subject will repeat these maneuvers a maximum of five times, and then be asked to perform 5 to 10 cough maneuvers of varying intensities while pressure at the esophageal balloon is recorded. The principal investigator's team has ample experience in esophageal manometry.

**Diaphragmatic Ultrasound:** A 7.5 MHz ultrasound (Acuson 128 XP/10, Mount View, Ca) linear transducer probe will be used to obtain 2D images (cross sectional view of the structure) of the diaphragm at the zone of apposition (ZOA) of the right hemithorax. All subjects will be seated comfortably in their wheel chairs during imaging. The diaphragm will be visualized in the right mid-axillary line at the levels of 8th or 9th intercostal space depending on a clarity and parallelism of visualized structures (pleura, diaphragm muscle and peritoneum). The diaphragm muscle in the ZOA is represented as a non-echogenic central structure bordered by two echogenic lines representing pleural and peritoneal membranes. Subjects will be asked to perform breathing through a flow volume meter (Carefusion, Yorba Linda, Ca) and to perform maneuvers of maximal inspiration and expiration. They will be asked to maintain an active respiratory effort in maximal inspiration and expiration for 1-2 seconds to prevent closure of the glottis and relaxation of the diaphragm and to provide a better visualization of the diaphragm in those positions. Continuous recording of the images will be obtained through at least 5 breathing cycles (maximal expiration to maximal inspiration). Simultaneous recording of time points and lung volumes will be obtained. All recordings will be done by the single experienced investigator. Retrograde analysis of the recordings will be done and freeze frame control will be used during replay alongside time records to precisely determine the end inspiration and end expiration. Diaphragm thickness (Tdi) will be measured as a distance between the midpoints of the pleural and peritoneal membranes at the end of inspiratory volume (EIV) and end of expiratory volume (EEV). The diaphragm thickness will be reported to the nearest 0.1mm which is within the range of accuracy of the transducer. The change in transdiaphragmatic index (Tdi) during inspiration (shortening of diaphragm), will be calculated and reported as the difference between Tdi at EEV and EIV, respectively.

**Randomization:** An independent investigator (unaffiliated with the pulmonary program and the present study) will generate a counter-balanced randomization table for enrolled participants. The randomization table will

account for equal sample sizes in the placebo and active drug group, and will be forwarded to the research pharmacy wherein the appropriate allocation of placebo/active drug will be dispensed and serve as the official study record.

**Weekly Home Pulmonary Function Assessment:** As a part of monitoring respiratory function, all subjects will be asked to perform weekly spirometry measurements using a portable spirometer [Microlife Digital Peak Flow & FEV1 Meter (Microlife Corporation, Dunedin, FL)]. This device will allow subjects to check and record peak flow and other relevant parameters of a forced expiration. Subjects will be given detailed instructions and a demonstration on a first visit to ensure their understanding of the device and the maneuvers they will need to perform. Upon turning on the device, subjects will be prompted to take a maximal breath in and then to exhale forcefully through a mouthpiece. Subjects will be instructed to close their lips around the mouthpiece to prevent air leak that could affect the measurement. The device will automatically record the results, and the dates and times of recording. All participants will be asked to perform three consecutive maneuvers preferably upon awakening in the morning.

**Weekly Self-symptom Survey:** Subjects will be asked to fill out a questionnaire [37] regarding their symptoms on a weekly basis, the responses for which will be entered into a master database on each visit.

**Bi-weekly phone interview:** A member of the investigative team will contact the subject over the phone on a biweekly basis to speak about any symptoms or changes in lung function that the subject may be experiencing or have experienced since a previous discussion. The phone interview will only last a few minutes. The subject will be reminded that they are allowed to contact a member of the study team at any point should they have a question or emergency.

**D. Data and Statistical Analysis:** The study design consists of two between factors (Treatment and SCI groups) and two within factors (Time). A mixed ANOVA will be used to determine main and interaction effects. Analyses will permit us to determine the effect of the drug treatment alone. We are expecting large effect sizes ( $d > 0.80$ ) for percentage increases in MIP among subjects receiving active drug versus placebo (see preliminary data above), therefore, the power is greater than 0.95 at  $\alpha < 0.05$ . Allowing for a 12 subject dropout, our power is still better than 0.85.

**E. Expected Results and Benefits:** We anticipate that administration of a beta-2 adrenergic agonist to a targeted cohort of individuals with tetraplegia and high paraplegia who have significantly reduced MIP at baseline shall result in significant improvements in surrogate indices of respiratory muscle strength and decreased work of breathing. It is also possible that anabolic effects might be sustained on follow-up testing 2 weeks after stopping test medication. Findings that a beta-2 adrenergic agonist improves inspiratory and expiratory muscle strength would have significant therapeutic implications by increasing cough effectiveness to help prevent mucus retention and atelectasis. Salutary effects would provide a rationale for a larger scale multicenter trial to assess if administration of beta-2 agonists is associated with a reduction in pulmonary complications, a major cause of morbidity and mortality in this population.

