Our intent in the present proposal is to enroll a targeted cohort of 24 comparatively weaker subjects with tetraplegia and high paraplegia in a randomized, double-blind, placebo-controlled, parallel group trial to assess the effects of an oral beta-2 agonist upon respiratory muscle strength and cough effectiveness. Based upon the findings from our recent study (please see "Preliminary Studies"), we have chosen a MIP of < 90 cmH2O as a criterion for study inclusion. Use of MIP as the preferred surrogate of underlying respiratory muscle strength in persons with SCI has been previously reported [14]. Individuals will be randomized equally (12 in each group) to receive oral albuterol versus matching placebo for 16 weeks (initial 4 weeks at previous dose of 4 mg twice daily, then in the absence of significant side effects, increased to 8 mg twice daily for the final 12 weeks). If we identify as we anticipate significant improvements in indices of respiratory muscle strength in the active study group after 16 weeks, we intend to repeat testing two weeks later to see if improvements are sustainable. Positive results would dictate the need to pursue a multicenter trial to see if pulmonary complications are reduced, thus making a significant impact on the welfare of this at risk population.

[figure not shown]

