Residual volume (RV) (L)	2.11±0.45	.89±0.41	1.98±0.44
Maximum inspiratory pressure (MIP) (cmH 2 O)	72.50±18.6	73.9±21.5	81.6±20.8*§
Maximum expiratory pressure (MEP)(cmH 2 O)	40.9±16.6	45.9±19.2	51.3±20.0*§

[figure not shown]
*data are mean±SD; \*p<0.01 versus baseline; §p<0.05 versus placebo; ●p<0.05 versus baseline; L=liters*

[figure not shown]
**Figure 1:** Percent change from baseline in MIP and MEP during phase 1 and phase 2. \* $p < 0.05$  for percent change from baseline.

washout period and into the placebo period (Figure 1), suggesting that sustained increase in MIP and MEP was due to improvement in respiratory muscle strength. Also, a significant increase in the ERV suggested that salmeterol improved expiratory muscle strength (Table 1) [33].

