Patients receiving salmeterol had significant improvement in FVC, FEV1, MIP, and MEP compared to placebo and baseline. Expiratory reserve volume improved during administration of salmeterol compared to baseline (Table 1, Figure 1). Because spirometric parameters improved consistent with bronchodilation, it cannot be stated for certain that improvement in MIP and MEP represented an increase in respiratory muscle strength because both parameters are highly dependent upon the lung volume at which they are measured. However, by considering MIP and MEP values in relationship to whether salmeterol was given first or second, it appeared that improvement in MIP and MEP among those given salmeterol first was sustained through the

**Figure 2:** Oral Beta-2 versus Placebo for a) % change in MIP from FRC, b) % change in MEP from TLC, c) % change versus baseline MIP in active; and d) % change versus baseline MEP in active.

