### C. Research Design and Methods:

**PROPOSED STUDY:** This prospective interventional study will be performed at the National Center of Excellence for Medical Consequences of Spinal Cord Injury located at James J. Peters Veterans Affairs Medical Center (JJPVAMC), Bronx, NY. Prior to patient recruitment, approval by the local Institutional Review Board and Research and Development Committee will be obtained. Written informed consent will be obtained from all participants prior to the screening. An oral beta-2 agonist, or placebo, will be administered to subjects with tetraplegia and high paraplegia; the study will be prospective, double-blind with placebo. Subjects will be selected who have no history of asthma, allergies, hypertension or cardiovascular disease. Also excluded will be those already using beta-2 adrenergic agonists, corticosteroids, or antidepressants. Twenty-four patients with tetraplegia (C3-C8) and high paraplegia (T1-T6) who have baseline MIP < 90 cmH2O if male or MIP < 65 cmH2O if female, will be studied. Participants with SCI will be selected from the approximately 120 individuals with SCI who undergo annual pulmonary function testing at our facility. These tests are routinely performed in our pulmonary function lab and interpreted by the principal investigator (~ 120 per year). We estimate that 65% of these subjects will have tetraplegia or high paraplegia (~ 78 subjects), and of these ~ 50% will have a MIP < 90 and 65 cmH2O leaving 39 subjects for enrollment; assuming an attrition rate of 30%, this leaves 27 subjects, more than the 24 anticipated, to complete the trial. Based on power analysis (provided below), we need 12 subjects in each group (albuterol vs. placebo) to have a power of 81% at the alpha of 5%. Subjects will be divided into two groups of twelve, randomized equally to receive sustained-release albuterol repeatabs versus matching placebo over a 16 week period. For the first week, the dosage of albuterol shall be 4 mg every 12 hours as in the previous trial, then in the absence of untoward side effects, increased to 8 mg every 12 hours for the remaining 15 weeks. The study drug/placebo will be dispensed by the VA Research Pharmacy on the subject's first visit and provided at no cost; both study investigators and subjects will be blinded as to study drug. Spirometric parameters, lung volume parameters, diaphragmatic thickness, maximal mouth inspiratory and expiratory pressures (MIP and MEP, respectively), simultaneously obtained esophageal pressure measurements (E-MIP, E-MEP), cough esophageal pressures (C-ESO) will be measured as described below at baseline, after 16 weeks and again at 18 weeks. The flow chart below highlights the test schedule:

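### Section D's mixed ANOVA does not say which term or visit decides the drug effect; name a week-16 between-arm contrast in MIP, adjusted for the baseline MIP already collected

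*Combined protocol and SAP*

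**What the plan says.** Section D (Data and Statistical Analysis) is the only analysis text. It describes the design thus: "The study design consists of two between factors (Treatment and SCI groups) and two within factors (Time"), then states "A mixed ANOVA will be used to determine main and interaction effects" and "Analyses will permit us to determine the effect of the drug treatment alone". No term is marked as decisive, no visit is named and no covariate is listed. The only scale mentioned is in the effect-size sentence, where d > 0.80 is expected "for percentage increases in MIP among subjects receiving active drug versus placebo".

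Other sections bear on the visits:

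- Background and Significance (last paragraph) looks for improvement in the active group after 16 weeks and, if it is found, "we intend to repeat testing two weeks later to see if improvements are sustainable".
- Section C says the outcomes "will be measured as described below at baseline, after 16 weeks and again at 18 weeks". Table 2 labels week 16 as Post and week 18 as Residual. Both schedule MIP at week 0.
- The inclusion criteria set upper limits on baseline MIP for men and for women.
- Section E places the follow-up test two weeks after the study drug stops.

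**The concern.** With Time as a single factor, the model has seven terms, and four contain Treatment: the main effect, Treatment x SCI group, Treatment x Time and the three-way term. Section D does not say which of them is the drug effect. It speaks of two within factors but names only Time and gives no levels.

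The later visits are not interchangeable, because week 16 closes treatment and week 18 is off drug. The scale is also unresolved. Percentage change from baseline is zero for everyone at week 0, so it cannot be the outcome of an ANOVA whose Time factor includes baseline.

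In a trial of 24 people, defensible readings of this plan can give different verdicts, and the choice between them could be made after the data are seen. A positive result is meant to justify a multicenter trial, so the deciding test should be fixed beforehand.

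**Working it through.** **Inputs from the documents.** Pilot percentage change in MIP (Section B): 22.7 ± 19.6 versus 7.5 ± 17.0, 15 per arm, p = 0.03. Planned size: 12 per arm, alpha 5% (Section C).

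**Assumptions.** Two-sided test. The pilot d carries over and applies equally to raw change. Variances are equal across visits, and visits are equally correlated at r = 0.5 to 0.9. The share of effect left at week 18 is 100%, 50% or 0%. The documents give neither r nor that share. Equal visit correlations make the week-16 and week-18 changes correlate exactly 0.5; other values c are tried below.

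**1. The plan's own figures.** Pooled SD = sqrt((19.6² + 17.0²)/2) = 18.35, so d = 15.2/18.35 = 0.829. At 15 per arm, t = 0.829 × sqrt(7.5) = 2.27 and p = 0.031, which matches the pilot. Section C's 81% does not reproduce with a two-sample t test: 12 per arm gives 0.47 at d = 0.80 and 0.49 at d = 0.829.

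**2. What Section D could mean.**

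- Time = baseline and week 16: Treatment x Time is exactly the unadjusted week-16 change test.
- Time = weeks 0, 16 and 18: Treatment x Time has 2 df and asks whether the profiles differ anywhere.
- Outcome = percentage change, so Time = weeks 16 and 18: the Treatment main effect is the average over both visits.

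**3. Power, 12 per arm.**

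- Week-16 change: noncentrality 0.829 × sqrt(6) = 2.03, df 22, power 0.49.
- Two-visit average: effective d = 0.829 × (1 + share kept)/2 / sqrt((1 + c)/2). At c = 0.5 this is 0.957, 0.718 or 0.478 (kept, half, lost), with power 0.61, 0.39 or 0.20.
- Treatment x Time over three visits, F(2,40): with the change SD set to 1, lambda = 12 × sum of squared deviations of the arm differences (0, d, share × d) from their mean. This is 5.49 if kept or lost and 4.12 if half kept, with power 0.51 and 0.40.
- Week 16 adjusted for baseline: the squared correlation of baseline with change is (1 − r)/2, that is 0.25 at r = 0.5 and 0.05 at r = 0.9. Adjusted d = 0.829/sqrt(1 − that) = 0.957 or 0.850, with power 0.61 or 0.51 (df 21, and the same to two decimals at df 20). Simulation with SCI group also in the model gives 0.59 to 0.49. Against 0.49 unadjusted, the gain is about 0 to 12 points.

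The pilot r² of 0.326 between baseline MIP and change is not used here. It comes from the 15 active-arm subjects only, in a trial not described as restricted by baseline MIP.

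**4. Disagreement between week-16 change and two-visit average (simulated).** At c = 0.5 the verdicts differ in 20% (kept), 19% (half) and 30% (lost) of trials. At c = 0.8 the figures are about 11%, 17% and 32%.

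**5. Type I error with no drug effect (simulated).** If either week-16 change or the two-visit average may count, it is about 0.07 at c = 0.5 and 0.06 at c = 0.8. If either the three-visit Treatment main effect or Treatment x Time may count, it is about 0.10 (1 − 0.95² = 0.0975).

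**The case against.** Read as a whole, the documents say more than Section D does. Background and Table 2 make week 16 the main result and week 18 the follow-up. Section D's effect-size sentence names percentage increase in MIP, active versus placebo, and refers back to a pilot comparison at one post-treatment test. So it would be wrong to infer that the plan gives no visit or scale at all. This stands. What remains is that the analysis text does not adopt the visit, that Background speaks of improvement in the active group rather than a between-arm contrast, and that the named scale does not fit a Time factor containing baseline.

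If Time means baseline and week 16 only, Treatment x Time is already a valid week-16 test. Most of the problem then reduces to saying so. This also stands, but the text does not settle on that reading.

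Averaging need not hurt. If the effect persists to week 18, it costs nothing (0.61 against 0.49). Section B hints at persistence: after salmeterol, "improvement in MIP and MEP among those given salmeterol first was sustained through the" "washout period and into the placebo period". Full loss is therefore a worst case.

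The power figures may be low for this cohort, since the plan expects weaker subjects to respond more and gives d > 0.80 as a floor. It gives no figure for that larger effect.

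A reader might infer that the plan's type I error is 10%, or 18% to 19% if any of the four Treatment terms may count. The documents do not support this. No such rule is stated, and counting SCI-group interactions as success conflicts with the stated aim of isolating the drug effect. A reader might also infer that the plan relies on the raw three-visit main effect, whose power would be only 0.06 to 0.35. Section D neither names raw MIP as the outcome nor calls that term decisive.

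**Conclusion.** The concern holds as a fault of specification with a concrete better method available. Section D leaves the deciding term and visit open and leaves out the baseline MIP it already has. On the stated assumptions (d = 0.83, 12 per arm, two-sided 5%), including week 18 by averaging moves power from 0.49 to anywhere between 0.61 and 0.20 at change correlation 0.5, depending on how much of the effect remains. Choosing afterwards between week-16 change and that average would put type I error at about 0.06 to 0.07. It reaches about 0.10 only under a permissive rule that the plan does not state.

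That no term is named and no covariate is planned is certain from the text. The size of the consequence is less certain, because it rests on visit correlations and persistence that the documents do not give. Treatment x Time is not an invalid test. Baseline adjustment is a modest gain that also guards against chance imbalance at entry. Neither change rescues the 81% power in Section C.

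**What to change.** In Section D, name one primary test: the active-versus-placebo difference in week-16 MIP in cmH2O, by ANCOVA with baseline MIP and SCI group as covariates, two-sided 0.05, with a 95% confidence interval. If the mixed model is kept, name its week-16 treatment contrast as the deciding term and list the levels of Time.

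Report percentage change in MIP and the week-18 contrast as secondary, and the SCI-group interactions as exploratory. State that MEP, esophageal and cough pressures, lung volumes and diaphragm thickness are secondary, since no outcome is now called primary.

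Restate the power basis in cmH2O, because the present d > 0.80 refers to percentage change.

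Separately, reconcile Background, where week-18 testing follows from improvement at week 16, with Section C and Table 2, where it is scheduled for everyone.

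The cost is a rewritten paragraph, a restated power calculation and one degree of freedom for baseline MIP, leaving 20 residual df with treatment, baseline and SCI group (24 − 4). No new data are needed.

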To pursue this question further, we recently completed a randomized, double-blind, placebo-controlled, parallel group trial in 30 persons with tetraplegia and high paraplegia (injury T6 and above). Fifteen subjects each in the active drug and placebo arms were randomized to receive an oral beta-2 agonist (albuterol repeat tabs 4 mg twice daily) versus matching placebo across 12 weeks (data not published). For post-intervention testing, we waited the equivalent of 5 half-lives of the drug to eliminate acute bronchodilator effects; any improvements in pulmonary function were therefore deemed secondary to increases in respiratory muscle strength. We found a statistically significant increase in MIP among subjects who received active drug versus placebo (%change =  $22.7 \pm 19.6$  vs.  $7.5 \pm 17.0$ ;  $p=0.03$ ). The corresponding change in MEP (active drug versus placebo) trended toward significance (%change=  $18.5 \pm 29.1$  vs.  $-0.2 \pm 19.8$ ;  $p=0.06$ ) [Figures 2a and 2b]. In the subset of individuals who received active drug ( $n=15$ ), a statistically significant inverse correlation was found between baseline MIP and change in MIP ( $r^2= -0.326$ ;  $p=0.03$ ), with a trend toward an inverse correlation between baseline MEP and change in MEP [ $(r^2= 0.181$ ;  $p=0.11$ ) [Figures 2c & 2d]. These findings suggest that those with the lowest baseline mouth pressures tended to have the greatest improvement in respiratory muscle strength after receiving oral albuterol (see shaded boxes, Figures 2c & 2d). Thus, administration of an oral beta-2 agonist appeared to elicit the greatest effect on respiratory muscle strength in the weakest individuals, thereby targeting those persons who conceivably stand to derive the greatest benefit. Upon further inspection, a cutoff baseline MIP value of 90 cmH2O identified subjects below which appeared to have the greatest responses to administration of active drug, while those with more “normal” MIP values above this threshold exhibited little improvement. Similar findings were noted with regard to MEP, but did not reach statistical significance. Albuterol was also very well tolerated with minimal side effects; one subject in the active drug group withdrew because of jitteriness.

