### **Human Subjects Involvement and Characteristics**

Subjects will be enrolled at the James J. Peters VA Medical Center for both the screening phase and the intervention phase. We estimate that a total of approximately 40 subjects will be recruited for the screening phase with about 24-27 meeting inclusion criteria and completing the study. All subjects will be studied at the James J Peters VA Medical Center within the Center of Excellence for the Medical Consequences of SCI. Subjects will be recruited from individuals that undergo annual pulmonary function testing within our Center (approximately 120 annually), of whom ~ 65% are anticipated to have cervical or high thoracic injury, and 50% of these also with reduced MIP (< 90 cmH2O).

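### The stated powers (81%, above 0.95, above 0.85) do not follow from the cited pilot effect, which gives about 49% with 12 per group

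*Combined protocol and SAP*

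**What the plan says.** Section C justifies the sample size by saying "we need 12 subjects in each group (albuterol vs. placebo) to have a power of 81% at the alpha of 5" per cent, and refers forward for the power analysis. The only power text that follows is in section D. It expects d above 0.80 "for percentage increases in MIP among subjects receiving active drug versus placebo (see preliminary data above), therefore, the power is greater than 0.95", and then adds: "Allowing for a 12 subject dropout, our power is still better than 0.85". Section D gives no sample size, SD, sidedness or within-subject correlation, and the 81% does not appear there.

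Three sample sizes can be read from section C: the 24 to be randomised, a recruitment pool, and the number left after attrition, described as "leaving 39 subjects for enrollment; assuming an attrition rate of 30%, this leaves 27 subjects, more than the 24 anticipated, to complete the trial". The section on human subjects likewise expects about 40 to be screened "with about 24-27 meeting inclusion criteria and completing the study".

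The preliminary data are in section B. The earlier oral albuterol trial, with 15 per arm, reports: "We found a statistically significant increase in MIP among subjects who received active drug versus placebo". The percentage changes were 22.7 ± 19.6 and 7.5 ± 17.0, with p = 0.03. Section B also reports that a baseline MIP cutoff of 90 cmH2O "identified subjects below which appeared to have the greatest responses to administration of active drug", but gives no mean or SD for that subgroup in the text.

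**The concern.** Section D presents its power as a consequence of the effect size and names the preliminary data as the source. Those data give an effect close to 0.80, and 12 per group is well short of 81% power for an effect of that size. Sections C and D also appear to disagree: if 81% and above 0.95 both describe the 24 randomised subjects, one of them is wrong.

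The 81% is the stated reason for 12 per group. The Background section makes the result decisive for the programme: "Positive results would dictate the need to pursue a multicenter trial to see if pulmonary complications are reduced". A reader who believes the stated power would take a non-significant result as evidence against an effect of the pilot's size, which the trial may not be able to provide.

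**Working it through.** **Inputs.** From section B: change in MIP 22.7 ± 19.6 (active) and 7.5 ± 17.0 (placebo), 15 per arm. From section C: 12 per group, alpha 5%, and the totals 24, 27 and 39. From section D: d above 0.80. Sidedness is not stated; two-sided is assumed, with one-sided also shown.

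**Step 1: the pilot effect.** Pooled SD = √[(19.6² + 17.0²)/2] = 18.35. Difference = 22.7 − 7.5 = 15.2 points. d = 15.2/18.35 = 0.83. Check: t = 0.829 × √(15/2) = 2.27 on 28 df, p = 0.031, which agrees with the reported 0.03. The 95% CI for d is about 0.07 to 1.57.

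**Step 2: which N each claim refers to.** Section C's recruitment arithmetic is 120 × 0.65 = 78; 78 × 0.5 = 39; 39 × 0.7 = 27.3, so about 12 are lost. This matches section D's 12 dropouts. The most charitable reading is therefore 81% at N = 24, above 0.95 at N = 39 and above 0.85 at N = 27. The plan does not say so; the assignment to 39 and 27 is an inference.

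**Step 3: power.** For a two-sample t-test of percentage change, the noncentrality is d√[n₁n₂/(n₁+n₂)] on n₁+n₂−2 df. For example, 12 + 12 at d = 0.829 gives 0.829 × √6 = 2.03 against a critical value of 2.07, so power is just under one half.

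| N (split) | Claim on this reading | d = 0.80, two-sided | d = 0.83, two-sided | d = 0.80 / 0.83, one-sided | d = 1.21, two-sided |
|---|---|---|---|---|---|
| 24 (12+12) | 81% | 0.466 | 0.492 | 0.600 / 0.626 | 0.809 |
| 27 (14+13) | > 0.85 | 0.515 | 0.543 | 0.646 / 0.673 | 0.855 |
| 39 (20+19) | > 0.95 | 0.682 | 0.712 | 0.790 / 0.814 | 0.957 |

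No entry at 0.80 or 0.83 reaches its claim, one- or two-sided. A simulation of 200,000 runs at d = 0.829 gave 0.492, 0.544 and 0.713.

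**Step 4: the effect that would be needed.** Two-sided, 81% at N = 24 needs d = 1.212, 0.85 at N = 27 needs 1.201, and 0.95 at N = 39 needs 1.186. One value, about 1.21, therefore covers all three claims. It corresponds to 1.21 × 18.35 = 22.2 points, and 1.21/0.829 = 1.46, that is 46% above the pilot. One-sided, the corresponding d is about 1.07.

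If instead above 0.95 refers to the 24 randomised, d must be 1.54 (1.541 × 18.35 = 28.3 points). If the 12 dropouts leave 12 of 24, power at the pilot effect is about 25%, and 0.85 would need d = 1.92.

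**Step 5: could the planned mixed ANOVA close the gap?** At the pilot effect with N = 24:

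- Adding the SCI-group factor (20 error df) gives 0.46 to 0.49 for d = 0.80 to 0.83.
- Averaging weeks 16 and 18, assuming a fully maintained effect and a correlation of 0.9 down to 0.5 (neither is in the plan), gives 0.51 to 0.61.
- Adjusting for baseline MIP, assuming the r² of 0.326 reported for the pilot's active arm held in both arms, raises d to 0.829/√(1 − 0.326) = 1.01 and gives 0.655 (0.71 at N = 27, 0.865 at N = 39). Reaching d = 1.21 would need R² of about 1 − (0.829/1.21)² = 0.53.

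**The case against.** The strongest reply is that 0.80 is a lower bound and the new trial differs from the pilot. It restricts entry to low MIP, where section B reports the larger responses, and it treats for longer with a planned dose increase. The pilot's interval for d also contains 1.21. A larger design effect is therefore plausible, and this part stands. But power that follows from a lower bound is only the power at that bound, which is 47% with 12 per group. The cutoff was also picked by inspecting the same pilot data, and no subgroup mean or SD is given, so the larger value needs to be stated and justified.

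A second reply is that section D may rest on a treatment-by-time interaction test. With f = 0.40 (equivalent to d = 0.80), two time points and an assumed correlation of 0.7, that calculation gives 0.998 at N = 24 and 0.90 at N = 12, satisfying both section D claims. It does not rescue them. With two time points the interaction test is the t-test on change, and this d is already standardised on change, so applying a correlation again counts the within-subject gain twice. The correlation appears nowhere in the plan, and the result contradicts the 81% for the same 24 subjects.

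It is also fair to say that d of about 1.2 is a reconstruction. One-sided testing combined with d of about 1.07, or strong baseline adjustment, would give similar figures. Each of these too is an unstated input.

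**Conclusion.** The concern holds. At the effect section D cites, 12 per group has about 49% power two-sided (63% one-sided), against 81% stated: a shortfall of about 32 percentage points. The claims above 0.95 and 0.85 fail at every sample size named in section C. The three figures can be made mutually consistent only by assigning them to different sample sizes and using an effect about 46% above the pilot's, or some other input the plan does not give.

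This rests on a two-sample comparison of percentage change at 5%, equal allocation and the pilot SD. It does not show that the trial will have 49% power: the effect in a low-MIP population may be larger, and the documents do not allow it to be estimated. It does show that the stated power does not follow from the stated basis. Since this is the only justification offered for the sample size, it should be corrected.

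**What to change.** Replace the power statements in sections C and D with one that gives N, d, SD, sidedness and test. For example: with 12 completers per arm and two-sided alpha 0.05, a two-sample comparison of percentage change in MIP has about 49% power for the pilot difference of 15.2 points (SD 18.3, from a trial not restricted to low MIP); 81% power requires a difference of about 22 points (d about 1.2).

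Then either remove the claims above 0.95 and 0.85, or state the N each refers to and justify the larger d, for instance from the pilot's low-MIP subjects. If baseline adjustment or a repeated-measures gain is relied on, state the assumed correlation and its source.

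Plan to report the treatment difference with its 95% CI, and to describe a non-significant result as inconclusive for effects of the pilot's size.

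The cost is rewording two paragraphs and a less favourable power figure unless a larger effect is justified. No extra enrolment or change to treatment is needed.
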